6.2.5 Follow-Up Period

6.2.5.1 End of treatment visit (EOT)

The EOT visit will be performed after permanent discontinuation of trial medication for any reason as soon as possible but no later 1 week after permanent discontinuation of the trial medication or when the investigator decided with the patient to permanently discontinue the trial medication or became aware that the trial medication had been terminated.

Proprietary confidential information.

© 2018 Boehringer Ingelheim International GmbH or one or more of its affiliated companies. All rights reserved.

This document may not - in full or in part - be passed on, reproduced, published or otherwise used without prior written permission.

Table 6.2.5.1: 1 Visit at the End of Treatment (EOT)

| | |
|---|---|
| ECG (Section 5.2.5) | Resting 12-lead ECG (digital) |
| Physical examination (Section 5.2.6.2) | A general physical examination as well as an orientated neurological examination will be performed, preferably by the same investigator throughout the study to enable comparability. This includes blood pressure, heart rate and temperature |
| | |
| Weight (Section 5.2.6.2) | Weight is measured; preferably, the same weight scale should be used throughout the study to ensure consistency of data collected. |
| Safety laboratory (Section 5.2.4) | Haematology, biochemistry, coagulation parameters, and urinalysis (dipstick). |
| Disease assessment: clinical and blood/MRI (Section 5.5.1) | Clinical: if patient has any new clinical symptoms of multiple myeloma, these should be recorded in the “disease assessment” page and as an AE when applicable (see Section 5.2.2.1). |
| | |
| Bone Marrow aspirate (Section 5.6.1) | 
Total body MRA should be performed.
 
The following assessments will be performed:
 
 • MM cells in bone marrow; percentage (%) of plasma cells in bone marrow should be assessed locally according to institutional standards and documented in eCRF. • BCMA expression by myeloma cells in bone marrow • MRD (in case M protein/FLC becomes undetectable) 
Obtain bone marrow biopsy if aspirate could not be obtained (punctio sicca). One sample of bone marrow will be provided for DNA banking.
 |

Proprietary confidential information.

© 2018 Boehringer Ingelheim International GmbH or one or more of its affiliated companies. All rights reserved.

This document may not - in full or in part - be passed on, reproduced, published or otherwise used without prior written permission.

Table 6.2.5.1: 1 (cont'd) Visit at the End of Treatment (EOT)

| | |
|--|--|
| Adverse events (Section 5.2.2) | Occurrence of AEs since last visit. |
| Concomitant therapies (Section 4.2) | Any new or any change in concomitant therapies since the last visit, will be recorded in the eCRF. |
| IWRS | Contact IWRS to register EOT. |
| Termination of Trial Medication | Including reason for conclusion, date of last administration of the trial drug. |

6.2.5.2 Residual effect period (REP)

The REP is defined in [Section 5.2.3](#). The End of REP (EOR) visit should not be performed earlier than 30 days after permanent discontinuation of the trial medication. The information collected at this visit should include all new AEs that occurred after EOT and a follow-up of adverse events ongoing at EOT. Any subsequent anti-cancer therapy administered between EOT and REP visit must be documented to allow an assessment of newly reported AEs as well as patient's status.

Table 6.2.5.3: 1 Residual effect period (REP)

| | |
|---|--|
| Adverse events (Section 5.2.2) | All AEs, SAEs, AESIs regardless of related ness. This includes all deaths. |
| Patient status | Collect information for progression or relapse, death, lost to follow-up. |
| Other therapy for Multiple Myeloma | In case the patient receives other therapy for Multiple Myeloma |

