| Body temperature | X | X | X | X | X | X | | X | X | X | X | X | | X | X | X | X | X | X | |
| Blood pressure (with heart rate) | X | X | X | X | X | X | | X | X | X | X | X | | X | X | X | X | X | X | |
| 12-lead ECG (local) ¹¹ | X | | | | | | | X | | | | | | X | | | | | | X |
| General safety laboratory parameters ¹² | X | X | X | X | X | X | X | X | X | X | X | X | X | X | X | X | X | X | X | |
| Screening for HCV, HBV, HIV | X | | | | | | | | | | | | | | | | | | | |
| Serum pregnancy test | X | | | | | | | X | | | | | | X | | | | | | X |
| Hospitalisation ⁷ | | X | | | | X ⁷ | | X | | | | | | X | | | | | | |
| Home Care Support ¹³ | | | X | X | X | X | X | X | X | X | X | X | X | X | X | X | X | X | | |
| Concomitant therapy | X | X | X | X | X | X | X | X | X | X | X | X | X | X | X | X | X | X | X | |
| Adverse events | | X | X | X | X | X | X | X | X | X | X | X | X | X | X | X | X | X | X | X |
| Eligibility for treatment | | X | | | | | | X | | | | | | X | | | | | | |
| Administration of BI 836909 | | X | c.i.v. | | | X | | X | c.i.v. | | | X | | X | c.i.v. | | | X | | |
| Disease / response assessment (clinical/MRI) ¹⁴ | X | | | | | | | X | | | | | | X | | | | | X | |
| Pharmacokinetics ¹⁵ | | see separate flow chart | | | | | | | | | | | | | | | | | | |
| Reason for treatment discontinuation / IWRS call | | | | | | | | | | | | | | | | | X | | | |
| Next line of anti-cancer therapy | | | | | | | | | | | | | | | | | | X | | |
| Patient status | | | | | | | | | | | | | | | | | | X | | |

1 each course has a duration of 6 weeks, 4 weeks of continuous infusion of BI 836909 and 2 weeks break.

[figure not shown]
- 2 EOT will be performed after permanent discontinuation of trial medication or as soon as possible but no later than 1 week after discontinuation of trial drug ([Section 6.2.5.1](#))
- 3 Follow up visit should be performed 30 days after the EOT (REP visit). In case of ongoing clinical benefit, patients can be followed up to collect data for duration of response. Follow-up visits for responders will be at 3, 6 and 12 months after EOT if a patient did not progress, started a new anti-cancer treatment, died, or withdrew informed consent.
Follow up visit after EOT: report all AEs, SAEs, AESIs regardless of relatedness. This includes all deaths unless due to underlying disease ([Section 6.2.5.2](#))
Extended follow up: report related SAEs and AESIs.

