Please note: Death should always be reported as SAE in this trial unless due to underlying disease.
- 4 in case of clinical benefit a maximum of 5 cycles is administered. In case of ongoing clinical benefit up to a maximum of 5 additional treatment cycles can be given if considered indicated by the investigator ([Section 4.1.5](#)), visit 6 at day 36 must be performed for all cycles except the last one.
- 5 results from routine assessments (MRI) for multiple myeloma are accepted for screening if performed no later than 28 days before start of treatment ([Section 6.2.2](#))
- 6 ± 3 days
- 7 patients will be hospitalized in the first cycle for 3 or 4 days if first bag change will be performed in the clinic, on day 1 of cycle 2 for 24 hours, in patients within inpatient dose escalation at the time when dose is escalated also for 24 hours and in all subsequent cycles for 8 hours on day 1 of each cycle; patients will also be hospitalized at the end of cycle 1 (day 29); hospitalization may be prolonged in case a patient experiences a cytokine release syndrome or a severe AE ([Section 6.2.1](#)).
- 8 within 14 days before day 1 cycle 1 or on day 1 cycle 1 before start of treatment, when M protein/ Free kappa/lambda light chain (FLC) becomes undetectable during treatment, on day 29 of cycle 3 and at EOT
Karyotyping: recent analysis will be accepted for screening before start of treatment if performed within 3 months prior to start of study medication and in case that no therapy has been given between assessment of karyotyping and study medication; otherwise, a baseline karyotype should be performed at screening; subsequent karyotyping could also be performed in subsequent marrow samples (**tests to be done locally**).
Percentage (%) of plasma cells in bone marrow should be assessed locally according to institutional standards and documented in eCRF.
- 9 MRD (minimal residual disease assessment): when M protein/FLC becomes undetectable during treatment; day 29 of cycle 3 and EOT (tests to be done centrally).
- 10 Optional collection and bio-banking of a baseline bone marrow sample and a bone marrow sample on treatment when a complete response is reached.
- 11 at screening and at the beginning of each cycle (except for cycle 1).

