In the rare case that a female subject participating in this clinical trial becomes pregnant after having taken trial medication, the Investigator must report immediately (within 24 hours) the drug exposure during pregnancy (DEDP) to the Sponsor's unique entry point (country-specific contact details will be provided in the ISF). The Pregnancy Monitoring Form for Clinical Trials (Part A) should be used.

The outcome of the pregnancy associated with the drug exposure during pregnancy must be followed up and reported to the Sponsor's unique entry point on the Pregnancy Monitoring Form for Clinical Trials (Part B).

As pregnancy itself is not to be reported as an AE, in the absence of an accompanying SAE, only the Pregnancy Monitoring Form for Clinical Trials and not the SAE form is to be completed. If there is an SAE associated with the pregnancy then the SAE has to be reported on the SAE form in addition.

The ISF will contain the Pregnancy Monitoring Form for Clinical Trials (Part A and B).

Exemption to SAE Reporting

Disease Progression in oncology trials is a study endpoint for analysis of efficacy. Disease progression (malignant neoplasm progression, neoplasm progression) is exempted from reporting as a (S)AE. Progression of the subject's underlying malignancy will be recorded in the appropriate pages of the (e)CRF as part of efficacy data collection. Death due to disease progression is to be recorded on the appropriate CRF page and not on a SAE form.

Examples of exempted events of PD are:

- Progression of underlying malignancy (Progressive disease PD): if PD is clearly consistent with the suspected progression of the underlying malignancy as defined by the respective response criteria.
- Hospitalization/Procedures due solely to the progression of underlying malignancy (PD)

Clinical symptoms and/or signs of progression (with or without confirmation by objective criteria e.g. imaging, clinical measurement): if the symptom can exclusively be determined to be due to the progression of the underlying malignancy and does meet the expected pattern of progression for the disease under study.

Please note, when there is evidence suggesting a causal relationship between the drug and the progression of the underlying disease, the event must be reported as (S)AE.

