Table 6.1: 2 Definition of treatment periods

Analyzing Treatment Period	Start Date	Start Time	End Date
Screening	Date of informed consent		Date of the first administration of BI 836909
Treatment	Date of the first administration of BI 836909	Time of the first administration of BI 836909	Date of the last administration of BI 836909
Residual effect period	Date of the last administration of BI 836909 + 1 day		Date of the last administration of BI 836909 + 30 day
Post-treatment	Date of the last administration of BI 836909 + 31 day		Not applicable

For safety analyses, adverse events (AEs) will be classified to one of the following time periods: “Screening”, “Treatment”, or “Post-treatment”. Section 5.2.2 of the protocol specifies that all AE reported within 30 days of the last trial medication will be considered on treatment. Detailed rule for assigning AEs to these time periods are listed below:

- If the date of informed consent \leq AE onset date $<$ date of first administration of BI 836909, then the AE is assigned to “Screening”;
- If date of first administration of BI 836909 \leq AE onset date \leq date of last administration of BI 836909 + 30 days, then the AE is assigned to “Treatment”;
- If AE onset date $>$ date of last administration of BI 836909 + 30 days, then the AE is assigned to “Post-treatment”.

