7.8.1 Adverse events

Unless otherwise specified, the analyses of adverse events will be descriptive in nature. All analyses of AEs will be based on the number of subjects with AEs and NOT on the number of AEs.

For analysis multiple AE occurrence data on the CRF will be collapsed into an AE provided that all of the following applies:

- All AE attributes are identical (LLT, intensity, action taken, therapy required, seriousness, reason for seriousness, relationship, outcome, AE of special interest)
- The occurrences were time-overlapping or time-adjacent (time-adjacency of 2 occurrences is given if the second occurrence started on the same day or on the day after the end of the first occurrence).

For further details on summarization of AE data, please refer to [\[3, 4\]](#).

The analysis of adverse events will be based on the concept of treatment emergent adverse events. That means that all adverse events occurring between first drug intake till last drug intake + residual effect period will be assigned to the treatment. All adverse events occurring before first drug intake will be assigned to 'screening' and all adverse events occurring after the residual effect period will be assigned to 'post-treatment' (for listings only). For details on the treatment definition, see [Section 6.1](#).

According to ICH E3 [\[5\]](#), AEs classified as 'other significant' needs to be reported and will include those non-serious adverse events leading to treatment discontinuation or non-serious AEs leading to dose reduction.

An overall summary of adverse events will be presented. This summary will include the first 6 categories from the list below and AEs by highest intensity graded according to CTCAE (version 4.03).

The frequency of subjects with adverse events will be summarised by treatment, primary system organ class and preferred term (mention MedDRA levels to be displayed in the tables).

Separate tables will be provided for patients with each of the following AE categories:

- All AEs,
- DLTs (Course 1 only¹),
- DLTs (All courses),
- AEs leading to dose reduction,

- AEs leading to treatment discontinuation,
- Serious AEs,
- Drug related AEs,
- Drug related serious AEs,
- CTCAE Grade 3 or higher AEs,
- AEs leading to death,

[1]: Course 1 defined by from start of treatment to start of Cycle 2 or the last dose administration of BI 836909 during Cycle 1 + 30 days, whichever occurs earlier.

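### The REP visit table asks for all deaths with AEs and SAEs, while flow chart footnote 3 and Section 5.2.3 exempt deaths from myeloma, so serious, Grade 3 or higher and fatal AE counts can differ by site.

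*Protocol*

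**What the plan says.** The Protocol describes the reporting of deaths after end of treatment in several current places.

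- **Table 6.2.5.3: 1 (in Section 6.2.5.2), adverse event row:** "All AEs, SAEs, AESIs regardless of related ness. This includes all deaths". No exception is given. The row refers the reader to Section 5.2.2.
- **Same table, patient status row:** "Collect information for progression or relapse, death, lost to follow-up". Death therefore has its own place outside the adverse event row.
- **Flow chart, footnote 3, for the follow-up visit after EOT:** "This includes all deaths unless due to underlying disease". The footnote cites Section 6.2.5.2, the section that holds the table without the exception.
- **Note in the same footnote:** "Death should always be reported as SAE in this trial unless due to underlying disease".
- **Section 5.2.3, exemption to SAE reporting:** "Disease progression (malignant neoplasm progression, neoplasm progression) is exempted from reporting as a (S)AE", and "Death due to disease progression is to be recorded on the appropriate CRF page and not on a SAE form".

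SAP 6.1 sets the analysis window: "Section 5.2.2 of the protocol specifies that all AE reported within 30 days of the last trial medication will be considered on treatment". SAP 7.8.1 counts patients with events and plans separate tables for serious AEs, for CTCAE Grade 3 or higher AEs and for "AEs leading to death". SAP 6.1 has statistics tabulated by dose group.

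**The concern.** A patient who stops treatment for progression and dies of myeloma within the next 30 days falls under two instructions. By the visit table, the death is reported with the AEs and SAEs. By footnote 3 and Section 5.2.3, it is not. A coordinator who follows the footnote's cross-reference to Section 6.2.5.2 arrives at the opposite instruction.

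If sites differ, the serious, Grade 3 or higher and fatal AE tables mix two definitions. A difference between dose groups could then reflect which page a site worked from. The dose groups are small, so one death is visible in the percentages.

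**Working it through.** The plan states no figure to reproduce. The check compares the texts, traces the result to the tables and sizes one patient.

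**1. Texts side by side, for a death from myeloma after end of treatment**

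| Source (Protocol) | Report with AEs/SAEs? |
|---|---|
| Table 6.2.5.3: 1, adverse event row | Yes, all deaths |
| Flow chart footnote 3 | No, if due to underlying disease |
| Note in footnote 3 | Not an SAE, if due to underlying disease |
| Section 5.2.3, exemption | No SAE form, if due to progression |

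The table row cannot easily be read as mere status collection, because the patient status row already collects death. The row points to Section 5.2.2, where an AE that results in death is serious. It does not point to the exemption in Section 5.2.3; the paragraph above the table cites Section 5.2.3 only for the definition of the REP. All of these are current text; none comes from the amendment log.

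**2. Path to the tables**

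SAP 6.1 assigns an AE to treatment if its onset is no later than last dose + 30 days. A myeloma death reported as an AE in that window enters the fatal AE table. It also adds a patient to the serious table if that patient has no other serious AE, and to the Grade 3 or higher table if there is no other AE of that grade. The SAP text has no rule that removes, flags or splits deaths from progression.

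The EOT visit may be up to 1 week after stopping and the follow-up visit is 30 days after EOT, so the visit can fall after the SAP window. AEs with onset after the window are post-treatment and appear in listings only.

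**3. Size of one death**

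Change in a dose group's fatal AE rate = 100 / n percentage points.

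- n = 3 (first patients in a 3+3 cohort, Protocol 3.1): 100 / 3 = 33.3
- n = 6 (expanded cohort): 100 / 6 = 16.7
- n = 12 (6 patients plus up to 6 more at the MTD or recommended dose, Protocol 3.1): 100 / 12 = 8.3

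**4. What does not move**

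- *DLT counts and MTD:* a non-haematological DLT must be drug-related (Protocol 5.2.1.1). Progression with evidence of a drug cause is reportable under Section 5.2.3 as well, so both rules agree there.
- *PFS and DOR:* death is an event for both, and it is recorded under patient status whichever rule a site follows.
- *Drug-related AE and drug-related serious AE tables:* a myeloma death judged unrelated does not enter them.

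**The case against.** The strongest reply is that the intended rule is clear. Section 5.2.3 is the section on AE collection and reporting, it has a heading for this exemption, and footnote 3 and its note agree with it. The footnote cites Section 6.2.5.2, which suggests that the table was meant to carry the same rule. The table's sentence follows a phrase about relatedness, so it can be read as covering deaths whether or not they are drug-related. SAP 7.8.1 also refers to sponsor standards on AE summaries that are not available here and might deal with such deaths.

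Most of this stands as evidence of intent, and a careful site would probably follow Section 5.2.3. But no passage says that Section 5.2.3 overrides the visit table, and a site completing the visit works from the table. Inconsistent reporting is therefore possible, though not shown.

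Three stronger readings are tempting and should not be drawn.

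- *That dose selection is affected.* The MTD rests on cycle 1 DLTs, and under Section 3.1.1 the safety committee reviews all available clinical and safety data. Nothing says that it decides from the SAP's fatal AE table.
- *That the number of deaths can be read from the survival figures in Section 1.1.* With medians of 9 and 3 months and exponential survival assumed, the 30-day risk 1 − exp(−ln 2 × 30 / (median × 30.4375)) is 7.3% to 20.4%, or 3.7 to 10.2 of 50 patients. These are deaths from any cause in a refractory population, with every patient at that risk. They do not count misreported deaths, which also depend on how many sites follow the table. Inclusion criterion 4 further requires a life expectancy of at least 6 months.
- *That a single-patient cohort gives a 100-point swing.* A percentage on one patient says little, and SAP 6.1 lets the four lowest doses share a column in selected displays. With four patients in that column, one death is 100 / 4 = 25 points.

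**Conclusion.** The point holds as an inconsistency between current passages that reaches three planned safety tables. It concerns only deaths from myeloma with onset up to last dose + 30 days, at sites that follow the visit table rather than Section 5.2.3. Each such death changes a dose group's fatal AE rate by 33, 17 or 8 points at n = 3, 6 or 12. The serious and Grade 3 or higher rates change by the same amount only if the patient has no other event of that kind.

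The number of deaths affected cannot be estimated from the documents. No death need be lost, since patient status captures it. The matter is worth correcting because it makes the tables comparable across sites and doses; it is not a threat to the primary endpoints. The conclusion assumes that the sponsor standards cited in the SAP do not already separate deaths from progression.

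**What to change.** Reconcile the passages. In the adverse event row of Table 6.2.5.3: 1, replace the second sentence with the wording of footnote 3, "This includes all deaths unless due to underlying disease", and add a reference to Section 5.2.3. Keep deaths from progression under patient status, where PFS and DOR draw on them. The cost is one phrase and one cross-reference.

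As an optional safeguard for data already collected under either reading, SAP 7.8.1 can add a display by dose group of all deaths up to last dose + 30 days, split into disease progression and other causes. It uses data already collected and costs one table.

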6.2.5.3 Extended follow up

In case of ongoing clinical benefit, patients can be followed up to collect data for duration of response. Follow-up visits for responders will be at 3, 6 and 12 months after EOT if a patient did not progress, started a new anti-cancer treatment, died, or withdrew informed consent and will assess related SAEs and AESIs.

Proprietary confidential information.

© 2018 Boehringer Ingelheim International GmbH or one or more of its affiliated companies. All rights reserved.

This document may not - in full or in part - be passed on, reproduced, published or otherwise used without prior written permission.

7. STATISTICAL METHODS AND DETERMINATION OF SAMPLE SIZE

7.1 STATISTICAL DESIGN – MODEL

The dose escalation procedure is described in [Section 3.1.1](#). Cohorts of patients will be entered sequentially into escalating dosage tiers with the aim to identify the maximum tolerated dose of BI 836909.

This study is open-label, which allows the safety of each dosage of BI 836909 to be assessed before treating additional patients with higher doses. Patients will not be randomized; they will be assigned to the cohort that is being filled at the time the patient is ready to enter the trial.

